10.5.3 Analyses of Exploratory Endpoints

The analysis of the exploratory endpoints will be performed using the LDI analysis set for LDI endpoints, SPARCC Enthesitis analysis set for SPARCC endpoints, mNAPSI analysis set for mNAPSI endpoints, psoriasis efficacy analysis set and subgroups of subjects with the baseline BSA < 3%, ≥ 3% but < 10%, and ≥ 10% for sPGA and BSA summary analyses, and the full analysis set for the other efficacy endpoints unless otherwise specified.

For radiographic exploratory endpoints, data will be analyzed as observed with no imputation for missing data or for subjects who enter rescue treatment. In addition, data will be analyzed using LOCF imputation for missing radiographs and for subjects who enter rescue treatment as sensitivity analysis. Probability plots and mean change plots will also be produced based on observed data.

Analyses to other exploratory endpoints will be summarized descriptively only. For VLDA and DAPSA, additional analyses at week 24 will also be performed as described in [Section 10.5.2](#).

10.5.4 Biomarker Endpoints

Data collected on biomarkers may be analyzed to help characterize subjects who are most likely to respond positively or negatively to etanercept or methotrexate. If the study team decides to perform such an analysis, it will be considered exploratory and will be described in a separate analysis plan.

10.6 Safety Analyses

All safety analyses will be conducted using the safety analysis set. Subjects will be analyzed according to the actual treatment received. Subjects who meet the inadequate response criteria at or after week 24 have the opportunity to enter rescue therapy and begin receiving etanercept plus methotrexate. In order to accurately reflect the safety experiences in these subjects with respect to the treatment received during rescue therapy, all events experienced during rescue therapy will be summarized separately.

10.6.1 Adverse Events

The Medical Dictionary for Regulatory Activities (MedDRA) version 18.0 or later will be used to code all adverse events (AE) to a system organ class and a preferred term. All adverse event tables will be summarized by treatment group for the double-blind treatment period and the rescue therapy period. The subject incidence of AEs will be

summarized for all treatment-emergent AEs, serious AEs, AEs leading to withdrawal of investigational product, and fatal AEs.

Subject incidence of all treatment-emergent AEs, serious AEs, AEs leading to withdrawal of investigational product, and fatal AEs will be tabulated by system organ class and preferred term in descending order of frequency.

Summaries of treatment-emergent and serious AEs occurring in at least 1% of the subjects by preferred term in any treatment arm will be provided in descending order of frequency.

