#### 3.1.2 Inadequate Response

Inadequate response is defined by having < 20% improvement in their tender and < 20% in their swollen joint counts from baseline at or after week 24. This will be calculated automatically based on the joint count. Inadequate response may be assessed at a

regularly scheduled visit or at a disease assessment visit as described in [Section 7.2.5](#). All subjects that initiate rescue treatment must complete a disease assessment follow-up visit 4 weeks later to monitor for labs (see [Section 7.2.5](#) and [Table 1](#)).

Subjects randomized to the etanercept plus methotrexate arm that have an inadequate response will continue to receive the same treatment.

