A method of imputation where missing post-baseline efficacy data will be carried forward from the last non-missing post-baseline value for that endpoint.

Rescue Therapy

It is defined as subjects whose IP admin CRF forms indicate whether a subject receives rescue IPs or not.

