6.4 Study Time Intervals

Double-blind Treatment Period

The period of time beginning when a subject receives their first dose of IP through the first dose of rescue treatment, or end of study if they are never rescued. In case where a

subject is randomized but never dosed, the double blind period will start on the randomization date.

Rescue Therapy Period

The period of time between the first dose of open-label rescue therapy at or after week 24 through end of study.

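### Double-blind adverse-event percentages are crude while risk time is cut at rescue, so unequal rescue between arms would bias them, probably in favour of methotrexate monotherapy

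*SAP*

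**What the plan says.** SAP 10.6.1 sets the layout: "All adverse event tables will be summarized by treatment group for the double-blind treatment period and the rescue therapy period". The measure is a count of subjects: "Subject incidence of all treatment-emergent AEs, serious AEs, AEs leading to withdrawal of investigational product, and fatal AEs will be tabulated". Protocol 10.5.4 likewise plans subject incidence only.

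SAP 6.4 runs the double-blind period from first dose "through the first dose of rescue treatment, or end of study if they are never rescued". What happens after that point leaves the double-blind table, because under SAP 10.6 "all events experienced during rescue therapy will be summarized separately".

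Rescue depends on outcome. Protocol 3.1.2 defines inadequate response as "having < 20% improvement in their tender and < 20% in their swollen joint counts from baseline at or after week 24". The same section says that combination-arm subjects who meet this definition "will continue to receive the same treatment". For analysis, SAP 6.1 identifies rescue from whether the "IP admin CRF forms indicate whether a subject receives rescue IPs or not".

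SAP 10.6.4 plans a descriptive exposure summary by treatment group, including duration of dosing. It is not tied to the adverse-event tables and is not stated to be split by period. Neither document plans a person-time rate, a time-to-event summary, or an adverse-event table over a window common to all arms.

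**The concern.** A crude percentage compares arms fairly when they are observed for similar lengths of time. Here observation stops early for subjects who respond poorly, and the trial expects response to differ by arm. An arm with more rescue has less time in which an event can count, so its percentage falls for a reason unrelated to the drug's safety.

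The rescue-period tables do not restore the comparison. SAP 6.1 defines actual treatment in that period as etanercept plus methotrexate for everyone, so those tables contain no contrast with methotrexate monotherapy.

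At stake is how a reader interprets the side-by-side double-blind percentages. Part of any excess on the etanercept arms could be an artefact of follow-up, and a genuine excess on methotrexate could be partly hidden.

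**Working it through.** **Inputs from the documents.** Assumed week 24 ACR 20 response is 44% (methotrexate), 60% (etanercept) and 65% (combination), from Protocol 10.2 and SAP 3.2. Non-response is therefore 56%, 40% and 35%. Treatment lasts 48 weeks and rescue starts at week 24 or later. Non-serious events are reported to the end of treatment (Protocol 9.2.1), so 48 weeks is used as the horizon.

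**Inputs that are assumptions.** The documents state no rescue fraction and no adverse-event rate, so there is no planned safety figure to reproduce. I assume the same constant hazard in every arm, no early withdrawal, all rescue at week 24, 30% of methotrexate subjects rescued, and 48-week event risks of 30% and 60% in subjects never rescued. The other rescue fractions are scaled by planned non-response:

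- etanercept: 30% × 40/56 = 21.4%
- combination: 30% × 35/56 = 18.75%

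**Mean double-blind risk time** is 48 − 24r, where r is the fraction rescued: 40.8, 42.9 and 43.5 weeks for methotrexate, etanercept and combination.

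**Crude incidence** is 1 − [(1 − r)·S48 + r·S24], where S48 and S24 are the event-free proportions at weeks 48 and 24. Under a constant hazard S24 = √S48. The gap between two arms reduces to (difference in r) × (S24 − S48).

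- 30% risk: S48 = 0.700, S24 = 0.837, difference 0.137
- 60% risk: S48 = 0.400, S24 = 0.632, difference 0.232

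| 48-week risk | Methotrexate | Etanercept | Combination | Gap to etanercept | Gap to combination |
|---|---|---|---|---|---|
| 30% | 25.9% | 27.1% | 27.4% | 1.2 points | 1.5 points |
| 60% | 53.0% | 55.0% | 55.6% | 2.0 points | 2.6 points |

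**Sensitivity.**

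- Rescue half as frequent in every arm: the gap is linear in r, so each gap halves, to about 0.6 to 0.8 points and 1.0 to 1.3 points.
- Rescue at week 36 instead of week 24: about 0.6 to 0.7 points and 0.9 to 1.2 points.
- Equal rescue fractions: zero.
- Ceiling for week 24 rescue. A subject with under 20% improvement in both joint counts cannot be an ACR 20 responder, so week 24 rescue cannot exceed non-response of 56%, 40% and 35%. The differences in r are then 0.16 and 0.21, and the gaps are 2.2 and 2.9 points for the 30% event and 3.7 and 4.9 points for the 60% event.
- Combination-arm inadequate responders not cut, because their treatment does not change: the difference in r against methotrexate becomes 0.30, and the gap to combination rises to 4.1 points (30% event) and 7.0 points (60% event).

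**Effect of the alternatives.** With equal constant hazards, incidence over weeks 0 to 24 is the same in every arm (1 − S24, which is 16.3% and 36.8%), and the ratio of exposure-adjusted rates is 1.00.

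**The case against.** The strongest reply is that this is minor and partly visible already. Safety is descriptive with no formal testing (SAP 10.1), so no decision rule is affected. The period split has a sound reason, stated in SAP 10.6: it attributes events to the treatment then being taken. Post-rescue events are tabulated, not lost. The exposure summary would show a reader that dosing time differed. The gaps are also small beside sampling error. With 280 per arm, the 95% half-width for a difference is 1.96 × √(2p(1 − p)/280), about 7.6 points at 30% incidence and 8.1 points at 60%.

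All of this stands as a limit on importance. It does not remove the bias, which runs in one direction across all events when rescue is unequal. Nor can a separate exposure table correct preferred-term percentages.

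A second objection concerns the remedy. Exposure-adjusted rates remove the bias only if the hazard is roughly constant. If all events fell before week 24, crude percentages would already be fair, and dividing by mean follow-up would inflate the methotrexate rate by about 43.5/40.8 = 1.07 relative to combination. That objection is correct, and it is why the week 0 to 24 table should lead.

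Three stronger readings are tempting but not supported:

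- A reader might infer that methotrexate will look safer. That needs rescue rates that actually differ. The planned hypothesis concerns ACR 20, not rescue, and early withdrawal also changes risk time.
- A reader might assume a large contrast such as 30% against 10% rescued, which gives 0.20 × 0.137 = 2.7 points for the 30% event. No such figure is in the documents, and the planned non-response rates imply a ratio nearer 1.4 to 1 for methotrexate against etanercept (56/40).
- A reader might take these tables as the only between-arm safety comparison. SAP 10.6.2 also provides for laboratory summaries by visit and treatment, and visits before week 24 precede any rescue.

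**Conclusion.** The concern holds as a conditional bias of small to moderate size. Crude incidence and truncation at an outcome-driven rescue are both in the text, and nothing planned adjusts for their combination. On the plan's own response assumptions the likely direction is downward for methotrexate monotherapy relative to both etanercept arms.

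The illustrative size is about 1 to 3 points. It rests on equal constant hazards, an assumed 30% methotrexate rescue fraction at week 24, and rescue proportional to planned non-response. The gap to combination is larger if combination-arm inadequate responders stay in the double-blind period, a point the SAP leaves open. Events in weeks 0 to 24, the efficacy analyses and the type I error rate are untouched.

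**What to change.** In SAP 10.6.1:

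1. Add a week 0 to 24 (pre-rescue) table of adverse-event incidence by arm, and name it the main between-arm adverse-event comparison.
2. Beside the full double-blind percentages, show subject-years at risk and exposure-adjusted rates by arm, for treatment-emergent and serious events, with a note that these rates assume a roughly constant hazard.
3. State whether combination-arm subjects who meet inadequate response, and whose treatment does not change under Protocol 3.1.2, leave the double-blind period for these tables. Align SAP 6.1 and 6.4 with that statement.

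The separate rescue-period tables stay as they are. The cost is one extra table and a few columns from data already collected, so the output is slightly longer. Alpha, endpoints, sample size and clinical rules do not change.

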10.6.2 Laboratory Test Results

Laboratory parameters with grade 3 toxicity or above may be descriptively summarized by study visit and actual treatment received during the study. Shift tables of the worst on-study laboratory toxicity based on the Common Toxicity Criteria (CTC) grade relative to baseline may be tabulated for analytes of interest (ie, creatinine, total bilirubin, AST (SGOT), ALT (SGPT), hemoglobin, platelets, WBC, absolute neutrophil count, lymphocytes) by treatment group. Modifications to CTC version 4.0 used for this analysis are described in [Appendix C](#). Subject listings of grades 3 and 4 laboratory values will be provided.

10.6.3 Vital Signs

Vital signs may be descriptively summarized in baseline disease summaries, if there is unexpected safety finding.

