### **7.1 Schedule of Assessments**

**Table 1. Schedule of Assessments**

Weeks	30-day Screening	Treatment Period								Disease Assessment (DA)		30-day Follow-Up Safety (EOS) 
		0 (day 1)	4	8	12	16	24	36	48/ET	DA Visit e	DA Follow-up e	
GENERAL & SAFETY ASSESSMENTS												
Informed consent	X											
Randomization via IXRS		X										
Medical/Medication history	X											
Concomitant medications		X	X	X	X	X	X	X	X	X	X	
Adverse events		X	X	X	X	X	X	X	X	X	X	
Serious adverse events	X	X	X	X	X	X	X	X	X	X	X	X
Physical examination a	X	X			X		X	X	X	X	X	
Vital signs	X	X	X	X	X	X	X	X	X	X	X	
Weight	X	X							X	X	X	
Height	X											
LABORATORY ASSESSMENTS												
Pregnancy test (serum) b	X											
Pregnancy test (urine) b,c		X			X		X	X	X			
Tuberculosis testing d	X											
Hematology and chemistry profile	X		X	X	X		X	X	X	X	X	
Hepatitis B surface antigen & core antibody; Hepatitis C virus antibody f	X											
High Sensitivity C-reactive Protein		X	X	X	X	X	X	X	X	X	X	
Urinalysis	X								X			
Biomarker blood sample		X		X			X		X			
INVESTIGATIONAL PRODUCT DISPENSING												
Etanercept/placebo for etanercept dispensation		X	X	X	X		X	X		X g	X	
Methotrexate/placebo for methotrexate dispensation		X	X	X	X		X	X		X g	X	
Folic Acid h		X			X		X	X				
SUBJECT DIARY DISPENSING												
Dispense subject diary		X	X	X	X	X	X	X				
Review subject diary			X	X	X	X	X	X	X	X	X	
DISEASE ASSESSMENTS												
Swollen and Tender joint count	X	X	X	X	X	X	X	X	X	X	X	
Physician Global Assessment of Disease Activity (VAS 0 to 100)		X	X	X	X	X	X	X	X	X	X	
Leeds Dactylitis Index		X	X		X		X	X	X	X	X	
Spondyloarthritis Research Consortium of Canada (SPARCC) Enthesitis Index		X	X		X		X	X	X	X	X	
Modified Nail Psoriasis Severity Index (NAPSI)		X	X		X		X	X	X			
Static Physician Global Assessment of Psoriasis		X	X		X		X	X	X	X	X	
Body Surface Area		X	X		X		X	X	X	X	X	
Radiographs (hands, feet)		X					X		X			

Footnotes defined on next page

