### **7.3.7 Vital Signs**

The following measurements must be performed: systolic and diastolic blood pressure, heart rate, respiratory rate, and temperature. Subject must be in a supine position in a rested and calm state for at least 5 minutes before blood pressure assessments are conducted. If the subject is unable to be in the supine position, the subject should be in the most recumbent position as possible. The position selected for a subject should be the same that is used throughout the study and documented on the vital sign eCRF. The body region used to assess temperature for a subject should remain consistent throughout the study and documented on the vital signs eCRF. If abnormalities are found and they are considered an adverse event, record on the adverse event summary page.

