### **10.5.4 Safety Endpoints**

Safety endpoints will be summarized descriptively for all subjects by treatment group based on the safety analysis set. Subject incidence of all treatment-emergent adverse events will be tabulated by system organ class and preferred term. Tables of fatal adverse events, serious adverse events, adverse events leading to withdrawal from investigational product or other protocol-required therapies, and significant treatment-emergent adverse events will also be provided.

Laboratory parameters with grade 3 or above will be summarized by study visit and treatment group. Vital signs will be reported in baseline summaries. Shift tables of the worst on-study laboratory toxicity for analytes of interest based on Common Toxicity Criteria relative to baseline will be tabulated by treatment group (as described in the SAP).

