4.1.4 Safety Endpoints

- Adverse events
- Serious adverse events
- Laboratory parameters and vital signs

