10.1 General Principles

The primary analysis will be performed after all subjects have completed the week 48 assessments and the 30-day safety follow-up period and all data have been finalized.

Subject disposition, demographics, and baseline disease characteristics will be summarized descriptively by randomized treatment group.

For categorical endpoints, the descriptive statistics will contain the frequency and percentage. For continuous endpoints, the descriptive statistics will include the number of observations, mean, standard error, standard deviation, median, minimum, and maximum.

Treatment effect will be tested for the primary and key secondary endpoints using a Bonferroni-based gatekeeping chain procedure to control the family-wise 2-sided type one error rate at 0.05. The significance level for the analyses of other secondary endpoints and exploratory endpoints will be 0.05 without adjusting for multiplicity and the p-values for these endpoints will therefore be treated as a descriptive statistic only. Safety endpoints will be tabulated by actual treatment received during the study. No formal statistical testing will be performed for safety analyses.

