
13. Appendices

Appendix A. Technical Detail and Supplemental Information Regarding Statistical Procedures and Programs

Analysis Windows for Evaluations

Per protocol, visits are to be performed within 7 days of the protocol-specified study day. To allow for variations in scheduling, the following visit windows will be applied to selected efficacy and safety evaluations (ie, vital signs, laboratory evaluations) to assign a most appropriate nominal visit for analysis. If more than one assigned visit falls within the same defined window, the closest visit to the target day (ie, scheduled visit week $\times 7 + 1$) will be considered for analysis. If two assessment dates are the same distance from the target day, then the latest visit will be considered for analysis. If more than one evaluation on the same date and time, the average of the results will be used. Only laboratory results collected from the central laboratory will be averaged in the case of duplicate results.

Any visit that falls in an unscheduled visit for that assessment (eg, an enthesitis assessment done at week 16) will be excluded from the analysis.

Visit Windows for Radiographic Endpoints

| Visit Week | Target Day | Window Definition | Interval (days) |
|------------|------------|--|-----------------|
| Baseline | 1 | Last Evaluation prior to or on Study Day 1 | n/a |
| Week 24 | 169 | Study Day 15 to 252 | 118 |
| Week 48 | 337 | \geq Study Day 253 | n/a |

^a If results from baseline radiograph are not available, the results from scan taken on or before Study Day 14 will be considered as baseline values.

Visit window for SPARCC, Dactylitis, mNAPSI, sPGA, BSA

| Visit Week | Target Day | Window Definition | Interval (days) |
|------------|------------|--|-----------------|
| Baseline | 1 | Last Evaluation prior to or on Study Day 1 | n/a |
| Week 4 | 29 | Study Day 2 to 56 | 54 |
| Week 12 | 85 | Study Day 57 to 126 | 70 |
| Week 24 | 169 | Study Day 127 to 210 | 84 |
| Week 36 | 253 | Study Day 211 to 294 | 84 |
| Week 48 | 337 | \geq Study Day 295 | n/a |

Visit window for SF-36 and PASDAS

| Visit Week | Target Day | Window Definition | Interval (days) |
|------------|------------|--|-----------------|
| Baseline | 1 | Last Evaluation prior to or on Study Day 1 | n/a |

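### Vital signs are part of a listed safety endpoint and are measured at seven post-baseline visits, but the only specific reporting rules concern baseline, and the SAP makes even that summary optional and conditional

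*SAP*

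**What the plan says.** Protocol 10.1.1.4 and SAP 4.1.4 carry the same third item in their lists of safety endpoints: "Laboratory parameters and vital signs".

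The Schedule of Assessments (protocol Table 1) marks vital signs in 11 columns: "Vital signs X X X X X X X X X X X". These are screening, day 1, weeks 4, 8, 12, 16, 24, 36 and 48/ET, the disease assessment visit and its follow-up. Protocol 7.3.7 defines the measurements as "systolic and diastolic blood pressure, heart rate, respiratory rate, and temperature". It asks for a rested, supine reading, with the same position and the same temperature site kept throughout the study.

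On analysis, the documents say four things:

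- Protocol 10.5.4, general: "Safety endpoints will be summarized descriptively for all subjects by treatment group based on the safety analysis set".
- Protocol 10.5.4, on vital signs: "Vital signs will be reported in baseline summaries".
- SAP 10.1, general: "Safety endpoints will be tabulated by actual treatment received during the study".
- SAP 10.6.3, on vital signs: "Vital signs may be descriptively summarized in baseline disease summaries, if there is unexpected safety finding".

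SAP Appendix A, under the analysis windows, adds that "the following visit windows will be applied to selected efficacy and safety evaluations (ie, vital signs, laboratory evaluations").

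**The concern.** The safety objective is to evaluate etanercept and methotrexate. A summary taken before the first dose describes who entered the trial. It cannot say what happened on treatment. If SAP 10.6.3 is followed as written, the analysis may contain no vital-sign output at all. If its condition is met, the output produced is a baseline table, which cannot describe an on-treatment finding.

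At stake is the descriptive comparison of on-treatment blood pressure, heart rate, respiratory rate and temperature between the combination and the two monotherapies. The data would be collected under a standardized procedure from three blinded, randomized arms, with no stated plan to report them.

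**Working it through.** The plan gives no figure to reproduce. The check compares the relevant sections and counts visits.

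**1. Collection.** Table 1 has 11 marked columns. Two of these (screening and day 1) are pre-treatment and two are disease assessment visits, which leaves 11 − 2 − 2 = 7 scheduled post-baseline visits: weeks 4, 8, 12, 16, 24, 36 and 48. With the planned 840 subjects, full attendance gives 840 × 7 = 5,880 sets of readings. This is an upper bound, because dropout lowers it.

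**2. Windows.** Vital signs do not appear in the special window tables of SAP Appendix A (radiographs; SPARCC, dactylitis, nail and skin measures; SF-36 and PASDAS). They therefore fall under the last table, which has windows for exactly those seven weeks. The SAP provides for assigning post-baseline vital signs to visits.

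**3. Specified outputs.** Neither document specifies a post-baseline vital-sign table, change from baseline, shift table or listing. The count is 0 in the protocol and 0 in the SAP. Laboratory parameters share the endpoint item but are treated differently. Protocol 10.5.4 plans by-visit summaries of values at grade 3 or above, and shift tables. SAP 10.6.2 makes these optional but still commits to listings of grade 3 and 4 values.

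**4. Population.** SAP 10.4 summarizes baseline disease characteristics for all randomized subjects by randomized group. SAP 7.3 and 10.6 require safety analyses on the safety analysis set by actual treatment. Placing vital signs in baseline disease summaries therefore also moves them out of the safety analysis framework.

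**5. Change between documents.** The protocol commits to a baseline summary. The SAP makes it optional and dependent on an unexpected safety finding. SAP Section 11 says that only secondary or exploratory endpoints were changed, so this change to a safety endpoint is undeclared.

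**6. What the data could show (illustration only).** The 95% half-width for a difference between two arms in mean change is 1.96 × SD × √(2/n). The documents give no SD for systolic pressure, so 10 to 15 mmHg is assumed.

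| n per arm | SD 10 | SD 15 |
|---|---|---|
| 280 (full attendance) | 1.66 | 2.48 |
| 252 (280 × 0.90, the plan's 10% dropout) | 1.75 | 2.62 |

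Under these assumptions the trial could estimate an arm difference to within about 1.7 to 2.6 mmHg. Precision would be lower after week 24, when rescued subjects leave the double-blind period (SAP 6.4).

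**7. Rescue timing.** Appendix A windows count from Study Day 1. A subject rescued at week 24 (day 169) has a follow-up 4 to 5 weeks later, on days 169 + 28 = 197 to 169 + 35 = 204. That falls in the Week 24 window (days 141 to 210) and loses to the visit nearer day 169. By-visit rescue summaries therefore cannot reuse these windows.

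**The case against.** The strongest reply is that the documents already cover the point. Vital signs are a safety endpoint, and both general statements promise that safety endpoints will be summarized or tabulated by treatment. Neither specific sentence says that baseline is the only time reported, and the Appendix A windows show that post-baseline use was foreseen. This has weight. A reader might infer that the plan rules out any post-baseline result in any arm, and the documents do not support that. What they contain is a general promise and a set of windows on one side, and specific sentences confined to baseline on the other. The general statements name no vital-sign output, statistic or time point, so they do not settle the conflict. If post-baseline tables are intended, the specific sentences still need correction.

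Second, vital-sign abnormalities considered adverse events are recorded as such (protocol 7.3.7) and reach the adverse event tables for the double-blind and rescue periods (SAP 10.6.1). This stands and narrows the gap. What remains is a shift in group means, or readings beyond a threshold that nobody judged to be an event.

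Third, a reader might call the SAP condition circular, on the ground that a vital-sign shift cannot be the trigger if vital signs are not summarized. That goes too far. An unexpected finding could also come from adverse events or laboratory results. The sounder criticism is that the triggered output is a baseline table, which cannot answer an on-treatment question.

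Fourth, a reader might say that one of three safety endpoints goes unreported. Vital signs are only part of the third item, and its laboratory part has its own planned outputs.

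Finally, the documents name no vital-sign risk for either drug that makes a small shift a specific study question. This limits the importance of the gap but does not explain why a listed endpoint has no on-treatment output.

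**Conclusion.** The point holds as an internal conflict and a gap in descriptive safety reporting. Part of a listed safety endpoint is measured at seven scheduled post-baseline visits and windowed for analysis. Its only specific reporting rules are a baseline summary in the protocol and an optional, conditional one in the SAP. Neither can show an on-treatment effect, and the softening between documents is undeclared.

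The size is modest. The gap is group-level change and threshold crossings not reported as adverse events, from at most 5,880 planned assessments. Safety analyses involve no formal testing, so no hypothesis, alpha level or power figure is touched. The visit count and the comparison of sections rest on the documents alone. The precision illustration rests on assumed SDs and is not needed for the conclusion. The point deserves correction because the data and windows are already provided for.

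**What to change.** Replace SAP 10.6.3 and the vital-signs sentence in protocol 10.5.4 with a firm commitment on these lines:

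- **Double-blind period.** Observed values and change from baseline in systolic and diastolic blood pressure, heart rate, respiratory rate and temperature will be summarized descriptively by visit and actual treatment, on the safety analysis set, using the Appendix A windows. The default statistics for continuous endpoints in SAP 10.1 suffice, and their minimum and maximum show extreme values.
- **Rescue period.** Values will be summarized separately, in line with SAP 10.6. They should be timed from the start of rescue, or reported as last value and change, because the Appendix A windows count from Study Day 1.

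Delete the wording that makes the summary optional and conditional on an unexpected safety finding. Record the change in SAP Section 11. If counts of threshold crossings are wanted, the SAP must define the thresholds, since the documents give none for vital signs.

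If the sponsor does not intend to report on-treatment vital signs, the alternative is to remove them from the safety endpoint lists and state the reason.

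The cost is a few extra descriptive tables and a short timing rule for the rescue period. No new data, site work or testing is needed.
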